5.3 Discharge Criteria

The patient randomized to receive study drug should remain in the hospital until all 3 doses of study drug have been administered. The criteria for medically indicated discharge from the hospital are:

- Abdominal pain has resolved or is controlled with medications;
- Solid food is tolerated, which is defined as eating ≥50% of a low fat, ≥500 calorie solid meal without an increase in abdominal pain or vomiting;

• There is no clinical evidence of an infection necessitating continued hospitalization.

In the scenario where the PI or treating physician wants the infusion(s) to begin earlier than the 24 hour +/- 1 hour window (e.g. the patient is ready to be discharged before all 3 doses of study drug have been administered and / or to facilitate an infusion time where study personnel are available), the PI or treating physician should contact the medical monitor to discuss whether it is appropriate to begin infusion earlier (up to 6 hours earlier) than the 24 hour +/- 1 hour protocol window.

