CV no inotrope	SBP mmHg	≥90	<90 fluid responsive	<90 not fluid responsive	<90, pH <7.3	<90, pH <7.2

CV = cardiovascular Adapted from Banks 2013

Appendix 2. American Gastroenterological Association Institute Guideline on the Initial Management of Acute Pancreatitis

	Recommendation	Strength	Quality
1a.	In patients with AP, the AGA suggests using goal-directed therapy for fluid management. Comment: The AGA makes no recommendation whether normal saline or Ringer's lactate is used.	Conditional	Very Low
1b.	In patients with AP, the AGA suggests against the use of HES fluids	Conditional	Very Low
2	In patients with predicted severe AP and necrotizing AP, the AGA suggests against the use of prophylactic antibiotics	Conditional	Low
3	In patients with acute biliary pancreatitis and no cholangitis, the AGA suggests against the routine use of urgent ERCP	Conditional	Low
4	In patients with AP, the AGA recommends early (within 24 h) oral feeding as tolerated, rather than keeping the patient nil per os	Strong	Moderate
5	In patients with AP and inability to feed orally, the AGA recommends enteral rather than parenteral nutrition	Strong	Moderate
6	In patients with predicted severe or necrotizing pancreatitis requiring enteral tube feeding, the AGA suggests either NG or NJ route	Conditional	Low
7	In patients with acute biliary pancreatitis, the AGA recommends cholecystectomy during the initial admission rather than after discharge	Strong	Moderate
8	In patients with acute alcoholic pancreatitis, the AGA recommends brief alcohol intervention during admission	Strong	Moderate

AGA = American Gastroenterological Association; AP = acute pancreatitis; ERCP = endoscopic retrograde cholangiopancreatography; HES = hydroxyethyl starches; NG = nasogastric; NJ = nasojejunal

Adapted from Crockett 2018

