8.6.3 Main Analytical Approach

Time to solid food tolerance through Day 30 visit will be analyzed based on the Generalized Multiple Comparison Modelling (gMCP-Mod) approach described in Session 8.6.1.

Time to solid food tolerance is defined as the number of hours from the date and time of the SFISD for the patient to the first date and time the patient receives a solid meal that is tolerated. If the mealtime was not recorded, the mealtime will be estimated using the middle time of the meal serving interval.

Tolerating a solid meal is defined as eating \geq 50% of a low fat, \geq 500-calorie solid meal without an increase in abdominal pain or vomiting within the two hours of mealtime. In addition, to meet the definition, all subsequent meals during the hospitalization should not show an increase in abdominal pain or vomiting within the two hours of mealtime. If a procedure that could impact food tolerance is performed after a solid meal is initially tolerated that results in subsequent meals not being tolerated, the time of the initial tolerated meal will be considered in the calculation of the time to solid food tolerance. The procedures that impact food tolerance and/or its assessment are defined as (1) a procedure that requires a period of nil by mouth (2) a procedure and/or treatment that causes gastrointestinal dysfunction e.g., cholecystectomy, necrosectomy. The procedures performed after the initial food tolerance will be reviewed before the database lock to identify the procedures that could impact the time to the tolerated solid food. If the subject was not discharged from the hospital during the study and did not tolerate solid food, the time to solid food tolerance will be censored at the latest date and time of the hospital stay.

If a patient is discharged home without tolerating solid food, the daily record of the modified American Neurogastroenterology and Motility Society Gastrointestinal Cardinal Symptom Index Daily Diary (mGCSI-DD) at or after hospital discharge will be used in the calculation of the time to solid food tolerance. The patients who did not tolerate solid food while hospitalized will be considered as tolerating solid food at or after hospital discharge at 8am on the first of three consecutive days where the following 4 criteria are met for the mGCSI-DD:

Protocol CM4620-203 CONFIDENTIAL Page 17 of 31

- none for vomiting
- none or mild for nausea

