8.7.2 Time to Medically Indicated Discharge

The time to medically indicated discharge is the number of days from the SFISD to the first date of meeting the criteria defining medically indicated discharge:

- the patient tolerates solid food, as defined by the main analytical approach; and
- abdominal pain is controlled or resolved, which will be defined by a reduction in pain, as assessed by the PNRS scale, of ≥50% from the peak level in the first 24 hours and no use of opioids; and
- there is no clinical evidence of an infection requiring continued hospitalization.

In patients who do not meet the criteria for medically indicated discharge when discharged from the hospital, the time to medically indicated discharge will be defined as 8am on the first of three consecutive days where the 4 criteria are met for the mGCSI-DD as defined in 8.6.3. If a patient is discharged not meeting the criteria for medically indicated discharged and does not meet criteria for the mGCSI-DD or has not completed the mGCSI-DD, the time to medically indicated discharge will be censored at 168 hours. If the patient dies while hospitalized, the time to medically indicated discharge will be censored at Day 30.

The time to medically indicated discharge will be summarized using Kaplan-Meier analyses. The medians and quartiles of time-to-events will be summarized for each study group. The time to medically indicated discharge will be compared between each Auxora treatment group and placebo group using stratified log-rank test stratified by sex (male or female) and the risk for organ failure (higher or lower). Prohibited immunosuppressive medications or immunotherapies and treatment discontinuation will be ignored (treatment policy strategy).

Protocol CM4620-203 CONFIDENTIAL Page 19 of 31

The proportion and 95% CI of patients who meet the medical discharge criteria by the 96-hour visit and the date of discharge will be displayed using a Clopper-Pearson interval and will be compared between each Auxora treatment group and placebo group using a Cochran-Mantel-Haenszel test stratified by the eCRF recorded sex (male or female) and the risk for organ failure (higher or lower) based on eCRF data. Prohibited immunosuppressive medications or immunotherapies and treatment discontinuation will be ignored (treatment policy strategy).

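### SAP 8.7.2 gives two conflicting times of medically indicated discharge for a patient who meets all criteria in hospital and then fails the pain/opioid or infection criterion at discharge

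*SAP*

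**What the plan says.** SAP 8.7.2 defines the endpoint as the "number of days from the SFISD to the first date of meeting the criteria defining medically indicated discharge". There are three criteria: solid food tolerance as derived in 8.6.3; pain at least halved from its peak in the first 24 hours, with no opioid; and no infection that requires a longer stay.

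The next paragraph of 8.7.2 goes by status at discharge. Its rule opens with "In patients who do not meet the criteria for medically indicated discharge when discharged from the hospital". Such patients are timed at 8 am on the opening day of a three-day run of diary entries that satisfy the mGCSI-DD conditions of 8.6.3. If the diary is absent or does not qualify, "the time to medically indicated discharge will be censored at 168 hours".

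The planned analysis is Kaplan-Meier with a stratified log-rank test. 8.7.2 also plans the proportion meeting the criteria by the 96-hour visit and by the date of discharge, and a Matthews correlation that uses status on the day of discharge.

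Protocol 10.7 has only the date on which the Section 5.3 criteria are met. It has no rule based on status at discharge, and SAP Section 13 lists no change to this endpoint.

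**The concern.** The two rules classify patients differently. The first looks for the earliest qualifying date. The second looks at one moment, the discharge. They disagree for a patient who qualifies in hospital and no longer qualifies on leaving.

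This state will be visible in the data. Protocol 8.5 to 8.10 checks readiness at each visit with a 24- or 48-hour look-back, and 8.11 records it again at discharge. The documents also show how it could arise:

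- Early responders are asked to wait: "The patient randomized to receive study drug should remain in the hospital until all 3 doses of study drug have been administered". The third infusion starts at about 48 hours and lasts 4, so a patient ready earlier waits until about hour 52.
- Protocol 5.3 accepts pain controlled with medication, while the SAP criterion requires no opioid. A patient can leave in line with the protocol and fail the SAP criterion that day.
- Protocol Appendix 2 reproduces the guideline item "In patients with acute biliary pancreatitis, the AGA recommends cholecystectomy during the initial admission rather than after discharge". Opioid use after surgery is plausible. For food, 8.6.3 protects the earlier date against such procedures: "the time of the initial tolerated meal will be considered in the calculation of the time to solid food tolerance". 8.7.2 gives the pain/opioid criterion no such protection.

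At stake is a secondary endpoint that also carries the second primary objective (responders versus non-responders to early solid food). Two programmers could derive different Kaplan-Meier curves from the same data, and a choice made after unblinding would be post hoc.

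**Working it through.** **No plan figure to reproduce.** The documents give no median, event count or power for this endpoint. The 72 versus 144 hour medians and the 86% power belong to solid food tolerance.

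**Step 1: which criteria can lapse.** Under 8.6.3, later intolerance during the stay cancels the earlier food date, unless a procedure caused it, in which case the date stands. Either way food leaves one answer. Only a pain/opioid or infection lapse produces two times.

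**Step 2: the rules side by side.**

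| Patient | First-met rule | Discharge-status rule, read literally |
|---|---|---|
| A: criteria met at 60 h, opioid restarted, discharged at 84 h | event at 60 h | event at a later diary date, or censored at 168 h |
| B: criteria met at 190 h, then a lapse, discharged at 220 h, no qualifying diary | event at 190 h | censored at 168 h |

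Patient B is censored 22 hours before the observed readiness (190 − 168) and 52 hours before discharge (220 − 168).

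**Step 3: size on assumed inputs.** None of these inputs is documented for this endpoint: 54 per arm; exponential readiness times with medians of 72 and 144 hours, borrowed from the food endpoint; discharge 6 to 48 hours after the later of readiness and hour 44; a lapse share applied to all patients; diary recovery averaging 72 hours after discharge; 50% or 80% of lapsed patients with a qualifying diary and the rest censored at 168 hours; unstratified log-rank; 400 trials per setting. Each arrow runs from the first-met rule to the literal second rule.

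| Lapsed | Diary qualifies | Active median, h | Placebo median, h | Power, % | Patients per trial censored before own readiness |
|---|---|---|---|---|---|
| 5% | 50% | 75 → 81 | 151 → 158 | 93.0 → 89.5 | 0.8 |
| 5% | 80% | 74 → 79 | 150 → 157 | 94.5 → 94.0 | 0.4 |
| 10% | 50% | 75 → 86 | 150 → 166 | 93.2 → 88.2 | 1.6 |
| 10% | 80% | 76 → 87 | 152 → 164 | 92.2 → 90.0 | 0.6 |
| 20% | 50% | 74 → 101 | 148 → 180 | 95.0 → 87.2 | 3.3 |
| 20% | 80% | 75 → 99 | 150 → 175 | 94.8 → 87.8 | 1.3 |
| 30% | 50% | 76 → 120 | 149 → 199 | 96.0 → 81.2 | 4.9 |
| 30% | 80% | 75 → 114 | 149 → 188 | 95.8 → 86.2 | 2.1 |

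The simulation error of one power figure is about √(0.9 × 0.1 / 400) = 1.5 points, which is why the starting values vary.

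**Step 4: the two extremes.** A second set of 2,000 trials per setting allowed a lapse only when discharge came more than 24 hours after readiness. Lapse chances of 10, 20 and 30% then moved about 7, 13 and 20% of patients. With every moved patient given a diary date 0 to 48 hours after discharge, power stayed at about 93% and the active median rose by 6 to 15 hours. With every moved patient censored at 168 hours, power fell from 93% to 89, 83 and 75%. A separate run of that setup with 70% qualifying diaries gave about 91, 91 and 89%, against about 94%.

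**The case against.** The strongest reply is that a harmless reading exists. The second rule may be meant only to supply a time for patients who left without ever qualifying. The food rule in 8.6.3 works that way, since it speaks of patients who did not tolerate food while hospitalized. The proportion in 8.7.2 counted by the date of discharge is cumulative, and the protocol has only the date of meeting the criteria. This shows what the authors may have intended, and it supports the first-met reading. It does not settle the text: where the SAP means never in hospital it says so in 8.6.3, and 8.7.2 does not.

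A reader might infer several stronger claims that the documents do not support:

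- That the SAP expressly overrides the first-met date. No sentence says so; the literal wording merely permits it.
- That lapses will be common. No rate is given. The wait for the third dose matters only for patients ready before about hour 52, and Protocol 6.2 allows for discharge before three doses. The surgery route concerns biliary cases, whose share is not stated. A somewhat higher pain score is not enough: it must exceed half of the first-24-hour peak.
- That a hazard ratio is biased. None is planned for this endpoint.
- That power falls to 75 to 89%. This requires that no moved patient has a qualifying diary, although diaries are daily after discharge with weekly calls, and the diary conditions do not include opioid use.
- That the primary analysis is affected. The gMCP-Mod analysis of solid food tolerance is untouched. The simulations compare arms and say nothing about responders versus non-responders.

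**Conclusion.** The conflict is real and narrow. For a patient who met all criteria in hospital and then failed the pain/opioid or infection criterion at discharge, 8.7.2 supports two times and does not rank them. This is more than missing detail: applied as written, the second rule replaces an observed event with a later date or a censored time, and for patient B that censoring precedes the event.

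The number affected cannot be obtained from the documents. On assumed lapse rates of 5 to 30% and the borrowed medians, the active median moves from about 75 hours to between 79 and 120, and the placebo median from about 150 to between 157 and 199. Power is about unchanged if every moved patient has a qualifying diary soon after discharge. With 50 to 80% qualifying it falls by about 0.5 to 15 points in Step 3. These figures are a range under assumptions, not a forecast.

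**What to change.** In SAP 8.7.2, limit both the diary sentence and the 168-hour censoring sentence to *patients with no date of meeting all criteria up to and including the day of discharge*. Add that an observed first-met date is kept whatever the status at discharge. This agrees with Protocol 10.7. Keep status on the day of discharge for the Matthews correlation only; the planned proportion by the date of discharge is cumulative and should follow the first-met date.

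If the sponsor instead intends readiness that lasts until discharge, 8.7.2 should say so in place of the first-date wording and extend the procedure exception of 8.6.3 to the pain/opioid criterion. That option should also state how pain status is judged for discharges after Day 10 and before the Day 30 assessments, when no pain score is scheduled.

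The first option costs a few lines of SAP text and needs no new data. Either choice should be fixed before unblinding.

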8.7.3 Length of Stay in the Hospital

The number of days patients are in the hospital from the SFISD, including ICU stay and readmissions for any etiology, during the 30 Days of the study will be summarized by treatment groups and compared between each Auxora treatment group and placebo group using an analysis of variance model, which includes treatment group, the stratification factor of the eCRF recorded sex (male or female), and then the stratification factor of the risk for organ failure (higher or lower) based on eCRF data as the fixed effects in the model. The proportion of patients in each quartile of hospital stay (1-7 days, 8-14 days, 15-21 days, and 22-30 days) and the patients who remain hospitalized at Day 30 will also be summarized by treatment groups.

Two sets of analyses will be conducted. The first analysis is to assess patient benefit; the number of days in the hospital will be defined as 30 if the patient dies due to acute pancreatitis (composite strategy). The second analysis is to assess healthcare systems benefit; the number of days in the hospital before the patient's death will be used in the analysis (while alive strategy).

8.7.4 Re-hospitalization for acute pancreatitis (AP) Through Day 30

The date of each re-hospitalization and the reasons for re-hospitalizations will be collected for each patient. The proportion and 95% CI of patients who are re-hospitalized for either acute pancreatitis or the development of pancreatic necrosis/necrotizing pancreatitis through the Day 30 visit will be displayed using a Clopper-Pearson interval and will be compared between each Auxora treatment group and placebo group using a Cochran-Mantel-Haenszel test stratified by the sex (male or female) and the risk for organ failure (higher or lower) based on eCRF data. Prohibited immunosuppressive medications or immunotherapies and treatment discontinuation will be ignored (treatment policy strategy). If the re-hospitalization for acute pancreatitis status is unknown, the re-hospitalization for acute pancreatitis will be imputed as No.

The proportion and 95% CI of patients who are re-hospitalized for other causes through Day 30 will also be analyzed in a similar manner.

Protocol CM4620-203 CONFIDENTIAL Page 20 of 31

8.7.5 Change in Severity of AP by CTSI Score from Screening to Day 30

Independent reviewers will perform a blinded central review of Contrast Enhanced Computed Tomography (CECT) imaging data, or MRI imaging data, obtained at the Screening and Day 30 visits to assess the computed tomography severity index (CTSI). Independent review will be performed by two independent radiologists (primary review) using a consensus methodology.

If the patient undergoes additional CECTs or MRIs at the discretion of the PI or treating physician from randomization to the Day 30 visit, the CTSI data will be listed but not used in the analysis unless the Day 30 visit data are missing. If the Day 30 visit data is missing, the last available unscheduled post-treatment data will be used for the change from baseline at Day 30 analysis based on the LOCF method.

Shift tables will display changes in severity by CTSI score (mild, moderate, severe) from baseline compared to Day 30 by treatment groups.

Proportion of patients with moderate or severe AP by CTSI score at baseline who became mild AP at Day 30, and the proportion of patients with mild AP at baseline who become moderate or severe AP will be displayed and analyzed in the same way as the re-hospitalization for acute pancreatitis through Day 30.

8.7.6 Development of pancreatic necrosis ≥30% and >50%

The development of pancreatic necrosis ≥30% and >50% through Day 30 will be assessed by the independent reviewers in the same way as the CTSI score.

The proportion and 95% CI of patients who developed pancreatic necrosis ≥30% and >50% during the study will be displayed and analyzed in the same way as the re-hospitalization for acute pancreatitis through Day 30. If the Day 30 data is missing, the last available unscheduled post-treatment data will be used as pancreatic necrosis status at Day 30 based on the LOCF method.

The proportion and 95% CI of patients who developed necrotizing pancreatitis, defined as either pancreatic or peripancreatic necrosis, during the study will be displayed and analyzed in the same way as the re-hospitalization for acute pancreatitis through Day 30. If the Day 30 data is missing, the last available unscheduled post-treatment data will be used as pancreatic necrosis status at Day 30 based on the LOCF method.

8.7.7 Persistence of SIRS ≥48 Hours After the SFISD

The persistence of SIRS ≥48 Hours after the SFISD is defined by the presence of at least two of the following four criteria at the first visit 48 hours after the SFISD:

- Temperature $< 36^{\circ}$ C or $> 38^{\circ}$ C;
- Heart rate > 90 beats/minute;
- Respiratory rate >20 breaths/minute or arterial carbon dioxide tension (PaCO2) <32 mmHg;

Protocol CM4620-203 CONFIDENTIAL Page 21 of 31

• White blood cell count (WBC) >12,000 mm3, or <4,000 mm3;

The proportion and 95% CI of patients who developed persistence of SIRS ≥48 Hours After the SFISD will be displayed and analyzed in the same way as the re-hospitalization for acute pancreatitis through Day 30. If the patient is discharged before 48 Hours after the SFISD, the last available post-treatment data will be used to define the SIRS status at 48 hours after the SFISD based on the LOCF method.

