2.3 Efficacy Endpoints

- Primary endpoint
 - Time to solid food tolerance
- Secondary endpoints:
 - Solid food tolerance at 48 hours, 72 hours, and 96 hours after the Start of First Infusion of Study Drug (SFISD) and at discharge
 - Time to medically indicated discharge
 - o Length of stay in the hospital
 - o Length of stay in the ICU for patients admitted to the ICU
 - Re-hospitalization for AP by Day 30
 - o Change in severity of AP by CTSI score from screening to Day 30
 - o Development of pancreatic necrosis ≥30% and >50%
 - o The persistence of SIRS ≥48 hours after the SFISD
 - o Incidence, severity, and duration of organ failure
 - Mortality by Day 30
 - o Change in pain score and opioid use

• Exploratory endpoints:

- Development of infected pancreatic necrosis
- Development of sepsis
- o Hospital procedures for the management of pancreatic necrosis
- o Change in GCSI-DD score
- o Change in albumin
- Change in absolute neutrophil count (ANC)/absolute lymphocyte count (ALC) ratio and IL-6 levels
- o Change in urine neutrophil gelatinase-associated lipocalin (NGAL) levels

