4 SELECTION OF PATIENTS

4.1 Inclusion Criteria

All of the following must be met for a patient to be randomized into the study:

- 1. The diagnosis of AP has been established by the presence of abdominal pain consistent with AP together with at least 1 of the following 2 criteria:
 - a. Serum lipase > 3 times the upper limit of normal (ULN);
 - b. Characteristic findings of AP on abdominal imaging;
- 2. The diagnosis of SIRS has been established by the presence of at least two of the following four criteria:
 - a. Temperature $< 36^{\circ}$ C or $> 38^{\circ}$ C;
 - b. Heart rate > 90 beats/minute;
 - c. Respiratory rate >20 breaths/minute or arterial carbon dioxide tension (PaCO₂) <32 mmHg;
 - d. White blood cell count (WBC) >12,000 mm³, or <4,000 mm³, or > 10% immature (band) forms;
- 3. At least one of the following criteria is present:
 - a. A peripancreatic fluid collection or a pleural effusion on a CECT performed in the 24 hours before Consent or after Consent and before Randomization;
 - b. Abdominal examination documenting either abdominal guarding or rebound tenderness;
 - c. Hematocrit \geq 44% for men or \geq 40% for women;
- 4. The patient is \geq 18 years of age;
- 5. Lack of pancreatic necrosis, pancreatic calcifications, pancreatic pseudocysts and no evidence for previous necrosectomy or pancreatic surgery identified by CECT performed in the 24 hours before Consent or after Consent and before Randomization.
- 6. A female patient of childbearing potential who is sexually active with a male partner is willing to practice acceptable methods of birth control for 180 days after the last dose of study drug. A female patient must not attempt to become pregnant for 180 days;
- 7. A male patient who is sexually active with a female partner of childbearing potential is willing to practice acceptable methods of birth control for 180 days after the last dose of study drug. A male patient must not donate sperm for 180 days;
- 8. The patient is willing and able to, or has a legal authorized representative (LAR) who is willing and able to, provide informed consent to participate, and to cooperate with all aspects of the protocol.

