- Determine if the patient met the medically indicated discharge criteria in the previous 24 hours (see Section 5.3)
- Perform AE/SAE assessment
- Prior to the infusion of the third dose of study drug:
 - Draw blood samples for CBC, differential, platelets, Serum Procalcitonin and Serum Chemistries – analyze at local lab. Testing may be performed on blood drawn in the previous 12 hours.
 - O Draw blood sample for Serum IL-6 send to central lab. Testing may be performed on blood drawn in the previous 12 hours.
 - Obtain urine sample for Urine NGAL send to central lab. Testing may be performed on urine collected in the previous 12 hours.
- Start the infusion of third dose of study drug 48 hours (±1 hours) from the SFISD (see Section 5.3)
 - o Record the time that the infusion starts and finishes
- Assess whether patient discharge is upcoming and whether mGCSI-DD worksheets need to be dispensed per Section 8.12.10.

8.7 72 hours

For patients who remain hospitalized 72 hours from the SFISD:

- Record concomitant medications
- Record weight closest to the scheduled time of assessment
- Record vital signs closest to the scheduled time of assessment
- Record the patient's pain using the PNRS closest to the scheduled time of assessment
- Record SpO₂ and the FiO₂ (see Section 8.12.6) closest to the scheduled time of assessment
- Determine if, and when the patient tolerated solid food in the previous 24 hours (see Section 5.2)
- Determine if the patient met the medically indicated discharge criteria in the previous 24 hours (see Section 5.3)
- Perform AE/SAE assessment
- Draw blood samples for CBC, differential, platelets, Serum Procalcitonin and Serum Chemistries analyze at local lab. Testing may be performed on blood drawn in the previous 12 hours or + 2 hours from assessment.
- Draw blood sample for Serum IL-6 send to central lab. Testing may be performed on blood drawn in the previous 12 hours or + 2 hours from assessment.
- Draw blood sample for PK \pm 2 hours send to central lab

- Obtain urine sample for Urine NGAL send to central lab. Testing may be performed on urine collected in the previous 12 hours or + 2 hours from assessment.
- Assess whether patient discharge is upcoming and whether mGCSI-DD worksheets need to be dispensed per Section 8.12.10.

8.8 96, 120, 144, 168, 192, 216, 240 hours (±4 hours)

For patients who remain hospitalized 96, 120, 144, 168, 192, 216, and 240 hours from the SFISD:

- Record concomitant medications

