8.12.7 Laboratory Analyses

At Screening, a lipase, CBC, differential, and platelets, will be performed at the local lab. For eligibility purposes, the results of the CBC collected within 24 hours of consent or following consent but prior to randomization will be used to determine the presence of SIRS (see Section 8.12.13) and a Hematocrit collected as SOC within 12 hours of consent or following consent but prior to randomization may be used for Inclusion Criterion 3c.

CBC with Differential and Platelets will be performed at 24, 48 and 72 hours, and if the patient remains hospitalized, at 120, 168, and 216 hours following SFISD as well as at Day 30 assessment. These samples will be sent to the local laboratory for analysis.

Serum Chemistries and Serum Procalcitonin will be performed at Baseline, 24, 48 and 72 hours, and if the patient remains hospitalized, at 120, 168, and 216 hours following SFISD as well as at Day 30 assessment. These samples will be sent to the local laboratory for analysis.

CBC results that should be reported in the eCRFs include absolute or percent neutrophil and lymphocyte counts. Serum chemistries reported in CRFs should include sodium, potassium, chloride, bicarbonate, blood urea nitrogen, creatinine, glucose, calcium, phosphorus, as well as magnesium, total protein, albumin, alkaline phosphatase, alanine transaminase (ALT), aspartate transaminase (AST), total bilirubin, lactate dehydrogenase (LDH), total cholesterol, triglycerides, and creatine kinase (CPK).

If a site is unable to perform any of the laboratory tests because it is not offered at the site, it will not be performed on patients randomized at the site.

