8.12.13 Systemic Inflammatory Response Syndrome (SIRS)

The physician, or appropriately trained designee will determine the presence of SIRS at Screening. The most extreme value for each criterion in the 24 hours before consent may be used. SIRS is defined as the presence of at least 2 of the 4 criteria:

- Temperature $< 36^{\circ}$ C or $> 38^{\circ}$ C
- Heart rate > 90 beats/minute
- Respiratory rate > 20 breaths/minute or arterial carbon dioxide tension (PaCO2)
 32 mmHg
- White blood cell count (WBC) >12,000 mm3, or < 4,000 mm3, or > 10% immature (band) forms

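### SAP 8.7.7 leaves the band-forms limb out of the 48-hour SIRS definition without giving a reason, so one definable group of patients who have SIRS by the protocol is scored as not persistent

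*SAP*

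**What the plan says.** Protocol 2.3 lists the secondary endpoint "The persistence of SIRS ≥48 hours after the SFISD" and attaches no criteria to it there.

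The protocol has one SIRS definition, set out in inclusion criterion 2 (4.1) and again in 8.12.13: at least two of four criteria. The white-cell criterion is "White blood cell count (WBC) >12,000 mm³, or <4,000 mm³, or > 10% immature (band) forms" in 4.1 and "White blood cell count (WBC) >12,000 mm3, or < 4,000 mm3, or > 10% immature (band) forms" in 8.12.13. The two agree.

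SAP 8.7.7 says that persistence is "defined by the presence of at least two of the following four criteria at the first visit 48 hours after the SFISD". Temperature, heart rate and respiratory rate/PaCO2 match the protocol. The fourth criterion is "White blood cell count (WBC) >12,000 mm3, or <4,000 mm3", and the bullet ends there. SAP 13 lists one change from the protocol's planned analysis, on ICU length of stay.

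On data collection, Protocol 8.12.7 states that "CBC with Differential and Platelets will be performed at 24, 48 and 72 hours", and the 48-hour visit in Protocol 8.6 repeats the instruction: "Draw blood samples for CBC, differential, platelets". For data entry, 8.12.7 says "CBC results that should be reported in the eCRFs include absolute or percent neutrophil and lymphocyte counts". Bands are not named.

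**The concern.** Persistence means that the state present at entry is still present. It should therefore be judged by the definition that established the state. Here a patient can qualify for the trial through bands, show the same values at 48 hours, and be counted as no longer having SIRS.

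The SAP also tabulates the number of SIRS criteria met at Screening (8.3) and uses that number to form a subgroup (8.12). The protocol definition governs at Screening, so SIRS would carry two meanings within one report. Because no reason is given, a reader cannot tell whether the omission is a decision or a transcription slip. At stake is the meaning of one secondary endpoint.

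**Working it through.** The documents state no rate, power or sample size for this endpoint, so there is no planned figure to reproduce. The check compares the two rules.

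**Inputs.** Five yes/no findings: T (temperature), H (heart rate), R (respiratory rate or PaCO2), W (white count above 12,000 or below 4,000) and B (bands above 10%).

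- Protocol rule (4.1, 8.12.13): SIRS if T + H + R + [W or B] ≥ 2.
- SAP rule (8.7.7): SIRS if T + H + R + W ≥ 2.

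**Enumeration.** There are 2^5 = 32 combinations.

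- Protocol: the white-cell criterion is met in 3 of the 4 W/B pairs, and then at least one of T, H, R is needed (7 of 8 patterns), giving 3 × 7 = 21. It is not met in 1 pair, and then at least two are needed (4 of 8 patterns), giving 4. Total 25.
- SAP: W is met in 2 pairs, giving 2 × 7 = 14. It is not met in 2 pairs, giving 2 × 4 = 8. Total 22.
- Difference: 25 − 22 = 3. All three have W = 0, B = 1 and exactly one of T, H, R.

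A criterion met under the SAP is always met under the protocol, so the disagreement runs one way. With the limb restored, the rules agree on all 32. These are counts of combinations, not patient frequencies.

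**Example.** Heart rate 100, white count 9,000, bands 15%, normal temperature and respiration. The protocol counts two criteria, so the SIRS entry criterion is met. With identical values at 48 hours, the SAP counts one, and SIRS is scored as not persistent.

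**Effect on rates.** Let p be an arm's persistence rate under the protocol rule and b the proportion of that arm in the three combinations above. The SAP rate is p − b. The difference between an Auxora arm and placebo becomes (p_A − p_P) − (b_A − b_P). The documents give no value for b in any arm. If b is equal in the two arms, the difference does not change. If b is the same fraction of p in both, the difference shrinks by that fraction. Otherwise it can move either way.

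**The case against.** Section 8.12.13 is written for eligibility, and the schedule of events marks the presence of SIRS at Screening only. Protocol 10.7 leaves the details of other secondary endpoints to the SAP, and 8.7.7 supplies them. SAP 13 covers changes to the planned analysis; the protocol planned no specific SIRS analysis, so a missing entry there is weak evidence of error. A count-only rule can also be applied alike at every site. Bands are not among the named eCRF items, and 8.12.7 allows a site to omit tests it does not offer. Restoring the limb could make classification depend on the local laboratory.

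The point about laboratories stands and shapes the fix. It is also true that restoring bands would not make the two measurements identical: entry may use the most extreme value over the 24 hours before consent, whereas 8.7.7 uses one visit. The deferral to the SAP does not settle the matter. The SAP took over the protocol's two-of-four rule and three of its criteria unchanged, and the protocol offers no other SIRS definition. The result reads as the same definition with a piece missing.

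A reader might infer that any patient with unchanged values is misclassified. Only those who need bands to reach two criteria are. A reader might also infer that the treatment difference is diluted in proportion. That requires the band-only share of persistent SIRS to be equal across arms, and nothing in the documents supports it. The Phase 2a rates (5 of 14 on Auxora, 5 of 7 on supportive care alone; Protocol 1.5.2) cannot supply a magnitude either. They count SIRS lasting continuously for at least 48 hours, which is a different endpoint.

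**Conclusion.** The two texts conflict without explanation. Under the SAP, patients with a white count of 4,000 to 12,000, bands above 10% and exactly one other criterion are scored as not persistent although they meet the protocol's definition of SIRS. The direction is certain: persistence can only be under-counted. The size cannot be given from the documents, because they report no band frequencies at entry or at 48 hours. The rule is the same in every arm, so it does not by itself show bias between arms.

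The reach is one secondary endpoint. SIRS at 48 hours does not enter the primary gMCP-Mod analysis (SAP 8.6), the sample size (SAP 4) or the hierarchical composite (SAP 8.9). This is a minor point, worth correcting because correction is cheap. The conclusion assumes that persistence is meant to refer to SIRS as the protocol defines it. If the sponsor intended a count-only definition, what is missing is the statement and the reason.

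**What to change.** In SAP 8.7.7, add more than 10% immature (band) forms to the white-cell criterion, using the differential already drawn for the 48-hour visit. First confirm that the CBC page of the eCRF captures a band percentage, since 8.12.7 names only neutrophils and lymphocytes. State how a patient with no reported bands is classified.

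Report by arm how many patients have bands unreported and how many qualify only through bands. Give the count-only result as a sensitivity analysis, so that site differences in band reporting are visible.

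If bands cannot be captured, keep the count-only definition and declare it, with its reason, in SAP 13.

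The cost is a line of SAP text, at most one eCRF field, and a small table with one sensitivity analysis. The downside is that some local laboratories may not report bands, so the limb will be unavailable for some patients.
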